4.7.2 Adverse events

General common rules for adverse events

All adverse events (AEs) will be coded to a lower-level term (LLT), preferred term (PT), high-level term (HLT), high-level group term (HLGT), and associated primary system organ class (SOC) using the Medical Dictionary for Regulatory Activities (MedDRA) version in effect at Sanofi at the time of database lock.

The AEs will be analyzed in the following 3 categories:

- Pre-treatment AEs: AEs that developed, worsened or became serious during the pretreatment period.
- Treatment-emergent adverse events (TEAE)s: AEs that developed, worsened or became serious during the treatment-emergent period
- Post-treatment AEs: AEs that developed, worsened or became serious during the posttreatment period

Similarly, the deaths will be analyzed in the pre-treatment, treatment-emergent and post-treatment periods.

The primary focus of AE reporting will be on TEAEs. Pre-treatment and post-treatment AEs will be described separately.

An AE with incomplete or missing date/time of onset (occurrence, worsening, or becoming serious) will be classified as a TEAE unless there is definitive information to determine it is a pre-treatment or a post-treatment AE.

If the assessment of the relationship to IMP is missing for an AE, this AE will be assumed as related to IMP. If the severity is missing for 1 of the treatment-emergent occurrences of an AE, the severity will be imputed with the maximal severity of the other occurrences. If the severity is missing for all the occurrences, the severity will be left as missing.

The AE tables will be sorted as indicated in Table 6.

Table 6 - Sorting of AE tables

AE presentation	Sorting rules
SOC, HLGT, HLT and PT	By the internationally agreed SOC order and by alphabetic order of HLGTs, HLTs and PTs.
SOC, HLT and PT	By the internationally agreed SOC order and by alphabetic order of HLTs and PTs.
SOC and PT	By the internationally agreed SOC order and decreasing frequency of PTsa, b
SMQ/CMQ and PT	By decreasing frequency of SMQs/CMQs and PTs ^a
PT	By decreasing frequency of PTs ^a

a Sorting will be based on the venglustat 15 mg dose group

Analysis of all adverse events

The overview of TEAE with the details below will be generated:

- Any TEAE
- Any treatment emergent SAE
- TEAE leading to death
- Any TEAE leading to permanent intervention discontinuation
- Any treatment emergent AESI

The AE summaries of Table 7 will be generated with number (%) of participants experiencing at least one event. The all TEAE summary by Primary SOC and PT (and other safety summaries (eg, SAEs, deaths), if deemed needed after TEAE evaluation) will be performed by trial impact (disruption) due to Covid-19.

Table 7 - Analyses of adverse events

Type of AE	MedDRA levels
All TEAE	Primary SOC, HGLT, HLT and PT
	Primary SOC and PT
Common TEAE (>5% in any group)	Primary SOC and PT
TEAE related to IMP as per Investigator's judgment	Primary SOC and PT
TEAE by maximal intensity	Primary SOC and PT
Treatment emergent SAE	Primary SOC and PT
Treatment emergent AESI	Primary SOC and PT
TEAE leading to permanent intervention discontinuation	Primary SOC and PT
TEAE leading to death (death as an outcome of the AE as reported by the Investigator in the AE page)	Primary SOC and PT
Treatment emergent Covid-19 related AE	Primary SOC and PT

b The table of all TEAEs presented by SOC and PT will define the presentation order for all other tables (eg, treatment-emergent SAE) presented by SOC and PT, unless otherwise specified.

Type of AE	MedDRA levels	
Pretreatment AE	Overview ^a	_
Pretreatment AESI	Primary SOC and PT	
Post-treatment AE	Overview ^a	

a Will include the following AE categories: any AEs, any serious AEs, any AESIs any AEs leading to death, any AEs leading to permanent intervention discontinuation

Analysis of deaths

In addition to the analyses of deaths included in Table 7 the number (%) of participants in the following categories will be provided:

- Deaths during the treatment-emergent and post-treatment periods by reason for death
- Deaths in non-randomized participants or randomized but not exposed participants

Analysis of adverse events of special interest (AESIs)

Adverse events of special interest (AESIs) and other AEs of interest will be selected for analyses as indicated in Table 8. Number (%) of participants experiencing at least one event will be provided for each event of interest. Tables will be sorted as indicated in Table 6.

Table 8 - Selections for AESIs

AESIs and other AEs of interest	Selection
Pregnancy of a female subject or female partner of a male subject	e-CRF specific pregnancy page
Symptomatic overdose (serious or non- serious) with IMP	e-CRF specific symptomatic overdose page
Increase in alanine transaminase (ALT)	e-CRF specific AESI tick box on the AE page
New or worsening lenticular opacities and cataracts	e-CRF specific AESI tick box on the AE page
AE related to Covid-19 illness	SMQ COVID19

4.7.3 Additional safety assessments

4.7.3.1 Laboratory variables, vital signs and electrocardiograms (ECGs)

The following laboratory variables, vital signs and electrocardiogram (ECG) variables will be analyzed. They will be converted into standard international units.

- Hematology:
 - Red blood cells and platelets and coagulation: hemoglobin, hematocrit, erythrocyte count, platelet count, prothrombin time (PT), prothrombin international normalized ratio (INR), activated partial thromboplastin time (aPTT).

- White blood cells: white blood cell count, neutrophils, lymphocytes, monocytes, basophils, eosinophils.
- Clinical chemistry:
 - Metabolism: glucose, protein, albumin.
 - Electrolytes: sodium, potassium, chloride, bicarbonate, calcium.
 - Renal function: creatinine, blood urea nitrogen, serum cystatin C.
 - Liver function: alanine aminotransferase, aspartate aminotransferase, alkaline phosphatase, gamma glutamyl transferase, total and direct bilirubin.
 - Pregnancy test: Serum β-human chorionic gonadotropin (all female participants).
- Urinalysis:
 - Urinalysis for quantitative analysis: pH, specific gravity, proteins, and glucose.
- Vital signs: heart rate, systolic and diastolic blood pressure, weight.
 - For all seated BP measurements, SBP and DBP will be analyzed using the average of the 3 to 5 separate measurements at each visit.
- ECG variables: heart rate, PR, QRS, QT, and corrected QTc (according to Bazett/Fridericia).

Data below the lower limit of quantitation/detection limit (LLOQ) will be replaced by half of the LLOQ, data above the upper limit of quantification will be replaced by ULOQ value.

Quantitative analyses

For all laboratory variables, vital signs and ECG variables above, descriptive statistics for results and changes from baseline will be provided for each visit, the last value and the worst value (minimum and/or maximum value depending on the parameter) during the on-treatment period.

All laboratory parameters (except urinalysis parameters) and vital signs parameters (except weight and height) will be summarized using the analysis windows as defined in Table 12. Urinalysis, ECG and weight will be summarized by planned visit using central measurements only.

Analyses according to PCSA

Potentially clinically significant abnormality (PCSA) analyses will be performed based on the PCSA list in effect at Sanofi at the time of the database lock. For parameters for which no PCSA criteria are defined, similar analyses will be done using the normal range, if applicable.

For parameters defined as efficacy endpoints, PCSA summaries will not be provided.

Analyses according to PCSA will be performed based on the worst value during the treatmentemergent period, using all measurements (either local or central, either scheduled, nonscheduled or repeated).

For laboratory variables, vital signs and ECG variables above, the incidence of participants with at least one PCSA during the treatment-emergent period will be summarized regardless of the baseline level and according to the following baseline status categories:

- Normal/missing
- Abnormal according to PCSA criterion or criteria

For ECG, the incidence of participants with at least one abnormal ECG during the treatmentemergent period will be summarized regardless of the baseline level and according to the following baseline status categories:

- Normal/missing
- Abnormal

Additional analyses for drug-induced liver injury

The following additional analyses will be performed for drug-induced liver injury:

- A graph of the distribution of peak values of ALT versus peak values of total bilirubin during the treatment-emergent period will be provided.
- For each liver function test (eg, ALT), participants having experienced a PCSA (eg, ALT >5 ULN) will be summarized using the following categories: Returned to baseline PCSA status (or returned to value \le ULN in case of missing baseline) before last IMP dose, Returned to baseline PCSA status after last IMP dose, Never returned to baseline PCSA status, No assessment after elevation. This summary will be performed by categories of elevation (ALT >3, >5, >10, >20 ULN).

The incidence of liver related AEs will be summarized by study intervention group. The selection of PT will be based on SMQ Hepatic disorder.

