- i* Urinalysis includes urine dipstick and microscopy. Dipstick includes assessment of specific gravity, pH, protein, glucose, blood, ketones, bilirubin, urobilinogen, nitrite, and leukocyte esterase. Microscopy (central lab) includes detection of formed cellular elements, casts, bacteria, yeast, parasites, and crystals in centrifuged urine sediment. Dipstick will be done locally, if any parameter on the dipstick is abnormal, a urine sample should be sent to the central laboratory for quantitative measurement.
- j* Plasma samples for PK to be collected on Day 1 (3 ±1 hours, post dose), Month 1 (pre-dose and 3 ±1 hours post dose), Months 6 and 18 (pre-dose). At visits when a post-dose PK sample is to be collected, patients should take the study drug on site.
- k* Spot urine will be collected based on 3 samples from the Day -2, morning of the day of the site visit and from 24 hour urine sample (or sample provided for urinalysis on the day of the visit - for visits when collection of 24 hour sample is not required) (see [Section 9.4.3](#)).
- l* Urine will be collected to evaluate exploratory biomarkers, albumin, total protein, creatinine, electrolyte and osmolality. At selected sites, urinary exosomes will be isolated from the urine at Visits 3, 4, 5, and 7. Please refer to laboratory manual for collection instructions. Collection of 24-hour urine sample at Visits 5 and 7 will be performed only at selected sites that participate in isolation of urinary exosomes.
- m* The 12-lead ECG recordings should be performed before blood samplings. Investigator should evaluate V2 ECG reading prior to run-in medication administration; V2 ECG central reader's assessment should be evaluated prior to IMP administration at Visit 3. The ECG will be evaluated as "normal" or "abnormal".
- n* Using a central reader, liver volume and combined renal volume of both kidneys will be measured. Combined renal cyst volume and renal parenchyma may be determined at a later date for a subset of patients.

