#### 9.4.7 Laboratory safety variables

All laboratory data listed in this section will be measured at a central laboratory. The laboratory data will be collected at designated visits as shown in [Section 1.3](#) and [Section 1.4](#). The clinical laboratory data consist of blood analysis (including hematology, clinical chemistry, and urinalysis). Clinical laboratory values will be analyzed after conversion into standard international units. International units will be used in all listings and tables.

The following laboratory safety variables will be analyzed:

- Hematology: red blood cell count, hematocrit, hemoglobin, white blood cell count with differential count (neutrophils, eosinophils, basophils, monocytes, and lymphocytes), platelets, prothrombin time (PT), partial thromboplastin time (PTT), and international normalized ratio (INR).
- Chemistry:
  - Plasma/serum electrolytes: sodium, potassium, chloride, calcium, bicarbonate,
  - Liver function: ALT, AST, gamma-glutamyl transferase (GGT), alkaline phosphatase (ALP), total and conjugated bilirubin,
  - Renal function: urea, serum creatinine, serum cystatin C,
  - Metabolism: glucose, albumin, total proteins.
- Urinalysis and microscopy.
- At screening, serum  $\beta$ -HCG test for women of childbearing potential (WOCBP).

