#### **10.1.2.2 Visit 4, 6, 8, 10, 12/Month 1, 6, 12, 18, 24 (Day 30, 180, 360, 540, 720)**

Patients will receive either placebo or venglustat, orally, at the clinic.

Patients will be instructed to record any missing doses and pain medication used in their diary. The patient should bring their diary and any remaining capsules to each clinic visit. The site staff will review the patient diary during each clinic visit and record excursions from treatment into the eCRF.

The following activities will be performed:

- Whenever possible, the following scales and questionnaires should be done prior to clinical interaction with the Investigator:
  - BDI-II (Visits 6, 8, 10, 12),
  - BPI (Visits 4, 6, 8, 10, 12),
  - BFI (Visits 4, 6, 8, 10, 12),
  - PGIS (Visits 8, 10, 12),

- PGIC (Visits 8, 10, 12),
- EQ-5D-5L (Visits 6, 8, 10, 12).
- Review of concomitant medications.
- Review of current medical conditions, with AE/SAE reporting (if any).
- Collection of spot urine sample.
- Collection of home urine based on 24-hour collection.
- Review daily symptom diary for completeness.
- Review of missed dose log for compliance.
- Abbreviated physical examination (focus on areas important for assessment of AEs if necessary; Visits 4, 6, and 8).
- Complete physical examination at Visits 10 and 12.
- Record of body weight measurement at Visit 8.
- Vital signs.
- 12-lead ECG at Visits 6 and 12.
- Laboratory assessments.
  - Chemistry and hematology.
- Blood sampling for GSL markers.
- Blood sampling for biomarker analysis (not collected at Month 1 in Stage 2).
- Blood sampling for PK analysis:
  - Stage 1: pre-dose and 3 hours post-dose at Visit 4; pre-dose at Visits 6 and 10,
  - Stage 2: pre-dose and 3 hours post-dose at Visit 4; pre-dose at Visit 12.
- Biobanking blood sample (optional) at Visits 8 and 12.
- Urinalysis (local dipstick test) including glucose, protein, bilirubin, urobilinogen, pH, specific gravity, blood, ketones, nitrite, and leukocyte esterase. Central urinalysis will be performed if any abnormality is observed in the urinalysis dipstick test.
- Urinalysis with microscopy; (to be performed by a central laboratory).
- Ophthalmological examination
  - At Month 6 (Visit 6), Month 12 (Visit 8), Month 18 (Visit 10), and Month 24 (Visit 12): ophthalmological examination with pupil dilation

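### By-visit urinalysis summaries use central values only, but the protocol sends urine for central quantitation only after an abnormal local dipstick, so the tables describe a selected subset

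*SAP*

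**What the plan says.** SAP 4.7.3.1 lists the urine variables as "Urinalysis for quantitative analysis: pH, specific gravity, proteins, and glucose". For all laboratory variables, "descriptive statistics for results and changes from baseline will be provided for each visit", along with last and worst on-treatment values. The data source for the by-visit urinalysis summaries is then restricted: "Urinalysis, ECG and weight will be summarized by planned visit using central measurements only".

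The protocol describes where those values come from. The urinalysis footnotes of both flow charts (Section 1.3 footnote i, Section 1.4 footnote h) put all four variables on the dipstick, have the dipstick done locally, and add that "if any parameter on the dipstick is abnormal, a urine sample should be sent to the central laboratory for quantitative measurement". Section 10.1.2.2 repeats the condition for Visits 4, 6, 8, 10 and 12: "Central urinalysis will be performed if any abnormality is observed in the urinalysis dipstick test". Section 10.1.1.1 (Visit 1) and Section 10.1.2.3 (Visits 5, 7, 9 and 11) say the same. The footnotes describe the microscopy that is always central as looking for cells, casts, organisms and crystals.

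Protocol 9.4.7, which includes urinalysis and microscopy, says something different: "All laboratory data listed in this section will be measured at a central laboratory".

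Separately, the spot-urine row of both flow charts runs from Visit 3 to Visit 13 with no dipstick condition. Footnote l for Stage 1 reads: "Urine will be collected to evaluate exploratory biomarkers, albumin, total protein, creatinine, electrolyte and osmolality". The Stage 2 footnote differs only in leaving out exploratory biomarkers at Month 1.

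**The concern.** A by-visit table in a safety report is read as a description of the treatment arm. If a central value exists only when a dipstick was abnormal, the table describes dipstick-positive patients at that visit instead. Who is in it depends on a result obtained after randomisation, which treatment may influence. The arms can then differ in how many patients contribute and in what kind of patient contributes, and randomisation no longer protects the comparison. The change from baseline is selected twice. Nothing in SAP 4.7.3.1 warns the reader that the values are conditional. In a kidney trial, urine protein is the variable where a misleading table would matter most.

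**Working it through.** The plan gives no figure for urinalysis to reproduce. The check is a reading of the passages, followed by an illustration of what the selection can do.

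**Reading the passages together**

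1. The SAP takes pH, specific gravity, proteins and glucose from central measurements only.
2. All four are on the local dipstick. Routine central microscopy, as the footnotes describe it, measures none of them.
3. Central quantitation is triggered when any of ten dipstick parameters is abnormal: specific gravity, pH, protein, glucose, blood, ketones, bilirubin, urobilinogen, nitrite, leukocyte esterase.
4. So a central value exists only for samples with at least one abnormality, though not necessarily in the variable being summarised.
5. Both flow charts schedule one pre-dose urinalysis, at Visit 1. A central baseline therefore normally needs an abnormal screening dipstick (an unscheduled sample could also supply one under SAP 5.4), and a change needs an abnormal dipstick at both times.

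**Illustration of the direction (all inputs are assumptions)**

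Let the marker in placebo patients be N(0,1) and in active patients N(0.50,1). Let *p* be the placebo share above the marker's own dipstick threshold *c*, and *q* the share of samples with another parameter abnormal, independent of the marker. A sample is sent if either holds. With arm mean μ (0 or 0.50), P = P(X>c) and E = μP + φ(c−μ):

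mean among samples sent = [qμ + (1−q)E] / [q + (1−q)P]

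- *p* = 5%, *q* = 0 (own threshold only), c = 1.645. Placebo: 0.1031/0.05 = 2.063. Active: 0.2702/0.1261 = 2.142. Difference 0.08, **understated**.
- *p* = 5%, *q* = 20%. Placebo: (0.8 × 0.1031)/(0.2 + 0.8 × 0.05) = 0.0825/0.24 = 0.344. Active: (0.2 × 0.5 + 0.8 × 0.2702)/(0.2 + 0.8 × 0.1261) = 0.3162/0.3009 = 1.051. Difference 0.71, **overstated**.
- *p* = 60%, *q* = 20%, c = −0.253. Placebo: (0.8 × 0.3863)/(0.2 + 0.8 × 0.6) = 0.3091/0.68 = 0.455. Active: (0.1 + 0.8 × 0.6876)/(0.2 + 0.8 × 0.7744) = 0.6501/0.8195 = 0.793. Difference 0.34, **understated**.

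A simulation of 2,000,000 patients per setting gives the same visit-mean differences and adds the change from baseline. It assumes a within-patient correlation of 0.6, and that other-parameter status is carried over from baseline with probability 0.7 and otherwise redrawn.

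| Assumed situation | True difference | Visit-mean difference | Difference in change |
|---|---|---|---|
| Selection on own threshold only, *p* 5–60% | 0.50 | 0.08–0.24 | 0.21–0.37 |
| Selection on any parameter, *p* 5–60%, *q* 20–80% | 0.50 | 0.34–0.71 | 0.41–0.50 |
| 1 SD effect only in the 10% abnormal at baseline, own threshold | 0.10 | 0.29 | 0.53 |
| 1 SD effect only in the 30% abnormal at baseline, own threshold | 0.30 | 0.41 | 0.66 |

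The second row is the protocol's trigger. The share of patients with a central value also differs by arm: with *p* = 5% and *q* = 20% it is 24% on placebo and 30% on active treatment.

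**The case against.** Five points can be made for the plan.

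- **Protocol 9.4.7 says these data are central.** Sections 10.1.1.1 and 10.1.2.2 also list an unconditional central urinalysis with microscopy, so quantitative values might exist for everyone. The laboratory manual, which could settle this, is not part of the documents. The point stands as a reason to ask for reconciliation. It does not remove the problem, because two footnotes and three visit sections state the condition explicitly, and a conditional step would be pointless if every sample were quantified centrally anyway.
- **The PCSA analysis uses local and central values, scheduled or not.** This stands as a partial safeguard: patients crossing a threshold may show there. It covers worst-value incidence only, it pools normal and missing baselines, and the PCSA list is not shown, so which urine parameters it covers is unknown.
- **Urine protein is collected regardless of the dipstick.** True, but SAP 4.7.3.1 does not say which sample feeds its proteins variable.
- **Safety analyses are descriptive, with no testing (SAP 4.7), and the study had already been stopped for futility.** This stands, and it limits the importance of the point.
- **The selection may be mild.** If another parameter is abnormal in most samples, nearly everyone is measured: with *q* = 80% the visit-mean difference is 0.48 to 0.53 against 0.50. The documents do not give that share.

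A reader might infer that the planned table must understate a real rise in proteinuria or glycosuria. That follows only if samples are sent on the summarised marker's own abnormality. The protocol's trigger is any parameter, and under it the visit mean can be too small or too large. Nor would a rise be wholly hidden, given the PCSA incidence.

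**Conclusion.** On the footnote reading, the by-visit central means and changes for urine pH, specific gravity and glucose are summaries of a subset selected on a post-randomisation result. The same holds for protein unless its source is the spot urine. They should not be read as describing the arms. The size and sign of any distortion cannot be determined from the documents; the ranges above rest on assumed abnormality rates, correlation and effect pattern, and show only that both directions are possible. The conclusion also assumes that the conditional passages, not Protocol 9.4.7, describe what sites do. No efficacy endpoint or stopping rule depends on these tables. This is a cheap improvement to descriptive safety output.

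**What to change.** 1. **Protocol:** reconcile Section 9.4.7 with the urinalysis footnotes of Sections 1.3 and 1.4 and with Sections 10.1.1.1, 10.1.2.2 and 10.1.2.3, so that it is clear which urine values are local, which are always central and which are triggered.
2. **SAP 4.7.3.1, dipstick:** if local results are captured, report result categories by visit and shifts from screening, with all tested participants as the denominator.
3. **SAP 4.7.3.1, protein:** name the spot-urine total protein, albumin and creatinine, scheduled for all patients at Visits 3 to 13, as the source for urine protein.
4. **SAP 4.7.3.1, triggered central values:** move them to a listing, or keep the table with a title saying it is conditional on an abnormal dipstick and show the number tested and the number sent per arm and visit.

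The cost is SAP wording and table programming; no new procedure or sample is needed. If local dipstick results are not in the database, only protein is fully repaired, and pH, specific gravity and glucose remain as conditional summaries labelled as such.
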